Study drug treatment extension beyond these 30 days will be guided by a number of risk factors for relapse of the presenting TTP episode and must be accompanied by an optimization of the immunosuppressive treatment. The risk factors will include the ADAMTS13 activity profile (measured weekly), as well as other signs and symptoms of continued underlying disease activity, such as presence of inhibitors if measured as routine practice by the site. Continued study drug treatment should be given for additional 7-day periods with a maximum of 28 days for subjects whose ADAMTS13 activity profile remains below 10% based on weekly measurements and for subjects with other clinical signs of underlying disease. In parallel, optimization of the immunosuppressive treatment should be considered starting at the Week 3 visit of the 30-day post-daily PE period and includes reversal of corticosteroid tapering through increase or re-initiation of corticosteroid treatment, or start/continuation of other immunosuppressive treatment such as rituximab (to be used as per standard site practice). Study drug treatment extension should be stopped when ADAMTS13 activity shows a sustained upward trend of >10% and at the latest on Day 28 of the study drug treatment extension.

Recurrence of TTP episode

- Exacerbation is defined as recurrent thrombocytopenia after initial recovery of platelet count (platelet count $\geq 150 \times 10^9/L$ with subsequent stop of daily PE within 5 days), requiring re-initiation of daily PE, occurring during the first 30-days post-daily PE period.
- Relapse is defined as recurrent thrombocytopenia after initial recovery of platelet count requiring re-initiation of daily PE, occurring after the 30-days post-daily PE period.

Based on the mechanism of action and the available efficacy and safety results from study ALX-0681-2.1/10 (Phase II TITAN trial) it is considered desirable from both a treatment and exposure perspective (to maximize the number of subjects exposed to caplacizumab), to allow for crossover to open-label caplacizumab for subjects who experience a recurrence of the TTP episode.

Exacerbation

In case of a first exacerbation of the presenting TTP episode, subjects will receive open label caplacizumab together with daily PE irrespective of what the initial treatment allocation was.

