Study Visit	Week 6 (+ 7 days after end of 30-day post-daily PE period) (± 1 day)	Week 7 (+14 days after end of 30-day post-daily PE period) (± 1 day)	Week 8 (+ 21 days after end of 30-day post-daily PE period) (± 1 day)	Week 9 (+ 28 days after end of 30-day post-daily PE period) (± 1 day)	Second or subsequent recurrence visit (At the time of initiating daily PE) ^b
Study drug administration (daily) ^c	x	x	x		
Corticosteroids	x	x	x	x	
Review of patient diary	x	x	x	x	x
Neurologic assessment ^d	x	x	x	x	x
SMMSE	x	x	x	x	x
Clinically significant TTP event	x	x	x	x	x
Bleeding assessment ^e	x	x	x	x	x
Adverse events					→
Concomitant medication					→
Platelet count ^f	x	x	x	x	x
Organ damage markers ^g	x	x	x	x	x
ADAMTS13 Activity	x	x	x	x	x
PK	x	x	x	x	x
PD parameters ^h	x	x	x	x	x
Immunogenicity (ADA) ⁱ				x	x

^a The following guidance with regard to timing of assessments planned at a single visit should be followed: s.c. study drug should be dosed after all other assessments have been performed.

After the last dosing in the treatment extension period, subjects are to complete assessments of the first and last FU visit as specified in [Table 3](#).

^b Also see section [3.1.1](#)

^c Study drug treatment should be administered s.c. for additional 7-day periods with a maximum of 28 days for subjects whose ADAMTS13 activity profile remains below 10% based on weekly measurements and for subjects with other clinical signs of underlying disease.

^d Neurological assessment will include assessment of the neurological system (including coma, stupor, seizures, disorientation/confusion, hemiparesis/-plegia, focal deficit, agitation, dysarthria).

^e Bleeding assessment is a clinical assessment of signs and symptoms of bleeding (e.g., petechiae, hematuria, epistaxis, meno-metrorrhagia, bruises) performed by the Investigator.

^f Samples for platelet count will be assessed by a local laboratory.

^g Organ damage markers include LDH, Troponin I, creatinine.

^h PD parameters include RICO, vWF:Ag, and FVIII:C.

ⁱ In case of a severe and/or serious hypersensitivity reaction, an additional blood sample to characterize the reaction should be collected as soon as possible after the start of the event.

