1.1.1. TREATMENT OF TTP

Plasma exchange therapy is the standard of care treatment for acquired TTP. It replenishes ADAMTS13, partially normalizing vWF processing, and removes pathogenic auto antibodies when present. Immunosuppressive treatment, most commonly corticosteroids, is started together with the PE therapy. Daily PE therapy is stopped (or tapered) when the platelet count has normalized for at least 48 hours. An "exacerbation" occurs in approximately 30% of patients [17]. Despite prompt initiation of daily PE and immunosuppressive treatment, acquired TTP still has an associated mortality of 10 to 20%. Severe ADAMTS13 deficiency (<10%) has been recognized as a potential biomarker for the management and follow-up relating to risk of relapse of acquired TTP patients [18, 19]. Although different thresholds for defining a severe deficiency in ADAMTS13 activity have been described, recent guidance papers have proposed a cut-off level of <10% to define a severe ADAMTS13 deficiency. ADAMTS13 levels below 10% during remission may predict an increased risk for relapse [20-22] and may be used as marker for active underlying disease [23].

In spite of recent advances in understanding the disease, there are no approved pharmacological therapies for acquired TTP. Caplacizumab represents a novel approach to the treatment microvascular thrombosis inherent in TTP and may provide significant benefit in terms of efficacy, safety and quality of life for subjects with TTP. Caplacizumab is being developed with the aim of preventing platelet consumption and formation of further microthrombi thereby reducing the duration of tissue ischemia and protecting the patient from the manifestations of the disease while the underlying process resolves.

[figure not shown]

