Results from the caplacizumab arm suggest that ADAMTS13 activity data could identify subjects who were at risk for early relapse. In 7 of 8 subjects with a relapse in the first month, it occurred within 4-10 days after stopping caplacizumab. All 7 subjects had ADAMTS13 activity values <10% at baseline, during and near the end of the treatment period, indicating unresolved underlying disease activity. In the 8th subject, the relapse event occurred at 30 days after stopping caplacizumab treatment. This subject had normalization of ADAMTS13 activity during and near the end of the treatment period. However at the time of the relapse, ADAMTS13 activity was again suppressed <10%, which suggests a *de novo* TTP event. Conversely, 22 caplacizumab-treated subjects did not have an exacerbation or relapse, with ADAMTS13 activity data available near the end of the treatment period for 16/22 patients. In 13 of 16 subjects without exacerbation or relapse, ADAMTS13 activity had returned to values \geq 10% near the end of the treatment. ADAMTS13 activity results from the placebo treated subjects supported the potential predictive value of the marker: for 14 of 16 placebo subjects without exacerbation or relapse (ADAMTS13 data available for 16/23 placebo subjects), ADAMTS13 activity values were \geq 10% near the end of the placebo treatment period. A total of 11 placebo subjects had an exacerbation during the treatment period, and ADAMTS13 activity data were available for 8 of them. Seven of 8 placebo subjects with an exacerbation had ADAMTS13 activity <10% around the time of the exacerbation, while the 8th subject had a borderline ADAMTS13 activity value of 11%. In summary, the data support ADAMTS13 activity as a potential marker to identify patients at risk for exacerbation or relapse, specifically patients with signs of ongoing active disease during the treatment period who are at risk of relapse early after stopping caplacizumab treatment.

No significant unanticipated safety concerns were raised for treatment with caplacizumab in this study. The results were as expected for the population of patients with acquired TTP. The overall duration of exposure to study drug was similar in the two treatment arms.

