3.3. TREATMENT OF SUBJECTS

Study drug treatment:

Daily PE period

- Loading i.v. dose: subjects will receive a single loading dose of 10 mg study drug by i.v. bolus injection from 6 hours to 15 minutes prior to the first PE done after randomization; also i.v. bolus of 10 mg caplacizumab (open label) will be given prior to the 1st PE for treatment of a first exacerbation during the 30-day post daily PE period or a first relapse during the treatment extension period (without a prior exacerbation).
- Daily s.c. dose: within 2 hours of completing each daily PE, a s.c. injection of 10 mg study drug will be administered daily throughout the full duration of PE treatment.

For more details on the study drug administration, please refer to section [3.3.5](#).

It is expected that subjects are hospitalized for the duration of the daily PE period. Exceptions should be discussed with the Medical Monitor.

30-day post-daily PE period

Daily s.c. administration of 10 mg study drug will continue for a period of 30 days after stop of daily PE. No adjustment to this period will be made for tapering of PE. Study drug should be administered at approximately the same time each day. Towards the end of the daily PE period and when hospital discharge is foreseen, subjects (or caregiver) should be trained in the s.c. self-administration of the study drug under the supervision of the Investigator or designee to allow for self-administration when at home. After discharge from hospital, subjects or caregiver will need to be able to self-administer s.c. study drug. For more details, please refer to section [3.3.5](#).

Treatment extension period

Study drug treatment extension beyond the 30 days will be guided by a number of risk factors for relapse of the presenting TTP episode and must be accompanied by an optimization of the immunosuppressive treatment. Study drug treatment should be extended for subjects who in the opinion of the Investigator have persistent active underlying disease for additional 7-day periods with a maximum of 28 days. In parallel, optimization of the immunosuppressive treatment should be considered at least at the Week 3 visit of the 30-day post-daily PE period and may include reversal of corticosteroid tapering through increase or re-initiation of corticosteroid treatment, or start/continuation of other immunosuppressive treatment such as rituximab (to be used as per standard site practice).

Decision on treatment extension

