The decision to extend treatment with additional 7-day periods should be made by the Investigator based on the ADAMTS13 activity profile, as well as other signs and symptoms

of continued underlying disease activity, such as presence of inhibitors if measured as routine practice by the site.

ADAMTS13 activity will be measured weekly and results of these analyses will be communicated to the clinical sites upon availability.

Study drug treatment extension should be stopped when ADAMTS13 activity shows a sustained upward trend of >10% or is stable and there are no other signs and symptoms of disease activity, and at the latest on Day 28 of the study drug treatment extension.

The reason for each weekly extension must be recorded in the electronic Case Report Form (eCRF).

Exacerbation

In case of a first exacerbation of the presenting TTP episode, subjects will receive open label caplacizumab together with daily PE irrespective of what the initial treatment allocation was. The blind will not be broken for the initial treatment allocation. Caplacizumab treatment and visit schedule will be the same as during the initial treatment period. In case a subject has subsequent exacerbations, standard of care treatment of daily PE and appropriate immunosuppressive treatment should be initiated as per site practice. There will be no re-initiation of study drug administration for a second or further exacerbation.

Relapse during the treatment extension period

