Study Visit	Week 6 (+ 7 days after end of 30-day post-daily PE period) (± 1 day)	Week 7 (+14 days after end of 30-day post-daily PE period) (± 1 day)	Week 8 (+ 21 days after end of 30-day post-daily PE period) (± 1 day)	Week 9 (+ 28 days after end of 30-day post-daily PE period) (± 1 day)	Second or subsequent recurrence visit (At the time of initiating daily PE) ^b
Study drug administration (daily) ^c	x	x	x		
Corticosteroids	x	x	x	x	
Review of patient diary	x	x	x	x	x
Neurologic assessment ^d	x	x	x	x	x
MMSE	x	x	x	x	x
Clinically significant TTP event	x	x	x	x	x
Bleeding assessment ^e	x	x	x	x	x
Adverse events					→
Concomitant medication					→
Platelet count ^f	x	x	x	x	x
Organ damage markers ^g	x	x	x	x	x
ADAMTS13 Activity	x	x	x	x	x
PK	x	x	x	x	x
PD parameters ^h	x	x	x	x	x
Immunogenicity (ADA) ⁱ				x	x

^a The following guidance with regard to timing of assessments planned at a single visit should be followed: s.c. study drug should be dosed after all other assessments have been performed.

After the last dosing in the treatment extension period, subjects are to complete assessments of the first and last FU visit as specified in [Table 3](#).

^b Also see Protocol Section 3.1.1

^c Study drug treatment should be administered s.c. for additional 7-day periods with a maximum of 28 days for subjects whose ADAMTS13 activity profile remains below 10% based on weekly measurements and for subjects with other clinical signs of underlying disease.

^d Neurological assessment will include assessment of the neurological system (including coma, stupor, seizures, disorientation/confusion, hemiparesis/-plegia, focal deficit, agitation, dysarthria).

^e Bleeding assessment is a clinical assessment of signs and symptoms of bleeding (e.g., petechiae, hematuria, epistaxis, meno-metrorrhagia, bruises) performed by the Investigator.

^f Samples for platelet count will be assessed by a local laboratory.

^g Organ damage markers include LDH, Troponin I, creatinine.

^h PD parameters include RICO, vWF:Ag, and FVIII:C.

ⁱ In case of a severe and/or serious hypersensitivity reaction, an additional blood sample to characterize the reaction should be collected as soon as possible after the start of the event.

Schedules of Assessments for Pediatric Subjects (Children/Adolescents)

Table 5: Time and events schedule for pediatric subjects: screening

Study Visit	Screening
Written informed consent /assent	x
Demographics	x
Medical history a	x
Review of eligibility criteria	x

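### The Section 3.3 stop rule lets an extension end when ADAMTS13 is merely stable, with no level given; read literally it stops subjects stable below 10% whom the synopsis and Table 4 continue

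*Protocol*

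**What the plan says.** **Stopping an extension.** Protocol Section 3.3 (Decision on treatment extension) has two ADAMTS13 triggers. One is a sustained upward trend of more than 10%. The other is introduced by "or is stable and there are no other signs and symptoms of disease activity". Day 28 of the extension is the outer limit. The synopsis (Treatment extension period) has only the first trigger: "Study drug treatment extension should be stopped when ADAMTS13 activity shows a sustained upward trend of >10% and at the latest on Day 28".

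**Continuing an extension.** The synopsis says that study drug "should be given for additional 7-day periods with a maximum of 28 days for subjects whose ADAMTS13 activity profile remains below 10" percent. It names subjects with other clinical signs as a second group. Table 4 footnote c gives the same two groups: "for subjects whose ADAMTS13 activity profile remains below 10% based on weekly measurements and for subjects with other clinical signs of underlying disease". The SAP copy of that footnote (Appendix A, Table 4) repeats it: "for subjects whose ADAMTS13 activity profile remains below 10% based on weekly measurements". Section 3.1.1 states the 28-day maximum and the risk factors, but has no stop rule and no 10% level.

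**What the extension is for.** Section 3.3 (Treatment extension period) says: "Study drug treatment should be extended for subjects who in the opinion of the Investigator have persistent active underlying disease". Section 1.1.1 says that "ADAMTS13 levels below 10% during remission may predict an increased risk for relapse", and that such levels may serve as a marker of active underlying disease. Section 1.2.4 reports that, in the Phase II caplacizumab arm, 7 of 8 subjects who relapsed in the first month did so 4 to 10 days after stopping drug. All 7 had activity below 10% at baseline, during treatment and "near the end of the treatment period, indicating unresolved underlying disease activity". Section 1.2.5 says this study will evaluate whether such patients benefit from longer treatment.

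**The concern.** Section 3.3 is the operative treatment section. A site that applies its second trigger as written would withdraw drug because a low ADAMTS13 value is not moving. Two other places in the protocol tell the site to keep treating for that same low value.

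Three things follow for a subject stopped in this way:

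- Study drug ends early in someone with the profile linked to early relapse in Phase II.
- Under Section 3.3, a first relapse while still on extension drug leads to open-label caplacizumab, but a relapse in follow-up does not. Stopping early gives up that eligibility sooner.
- SAP Section 4.4.1 (Table 1) ends the treatment period at the last extension visit. SAP Section 6.2.1 counts only relapses within that period for the first key secondary endpoint, so its window closes earlier too.

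**Working it through.** The plan has no figure to reproduce, so the check is to apply each rule to the same subject: on extension, before Day 28, with no upward ADAMTS13 trend.

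| ADAMTS13 course | Other signs | Synopsis | Table 4 footnote c | Section 3.3, literal |
|---|---|---|---|---|
| Stable below 10% | No | Continue | Continue | **Stop** |
| Stable below 10% | Yes | Continue | Continue | Continue |
| Stable at or above 10% | No | No reason to continue, but no stop trigger before Day 28 | No reason to continue | Stop |
| Stable at or above 10% | Yes | Continue | Continue | Continue |

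The instructions conflict only in the first row.

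**Can the wording be reconciled as it stands?** One route is to count activity below 10% as itself a sign of disease. That fails, because Section 3.3 lists the ADAMTS13 profile separately from other signs and symptoms, so *other* means other than ADAMTS13. A second route is to carry the 10% figure across to *stable*. Grammatically, however, the figure belongs to the trend.

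**Size per affected subject.** The inputs are the visit days in protocol Tables 3 and 4, counted from the end of daily plasma exchange and ignoring the ±1 day windows.

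- Week 5: Day 30
- Week 6: 30 + 7 = Day 37
- Week 7: 30 + 14 = Day 44
- Week 8: 30 + 21 = Day 51
- Week 9 (maximum): 30 + 28 = Day 58

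The clause stops an extension already under way, so the earliest stop after a complete 7-day period is Day 37. For a subject who would otherwise have stayed below 10% for all four weeks, days lost = 58 − stop day:

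- Stop at Week 6: 58 − 37 = 21 days
- Stop at Week 7: 58 − 44 = 14 days
- Stop at Week 8: 58 − 51 = 7 days

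**Where a relapse would fall.** Take a stop at Day 37 and the Phase II interval of 4 to 10 days. The relapse falls between Day 41 (37 + 4) and Day 47 (37 + 10). That is after the first key secondary window has closed, but within the 4-week follow-up, so the second key secondary endpoint still counts it.

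**With the level inserted.** If *stable* is limited to 10% or more, the first row becomes *continue* under all three texts. The other rows do not change.

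**The case against.** The strongest reply is that the intended meaning is fairly clear. Low ADAMTS13 is a main reason for extending, so stopping because the same low value persists would defeat the purpose. Three places say that drug should continue below 10%, one of them the schedule for the extension period itself. Every extension is the Investigator's decision, all these rules say *should*, and the reason for each weekly extension goes into the eCRF. Treatment duration would vary between subjects even with perfect wording. This largely stands, and it is why the point is minor. It does not remove the contradiction, because one *should* says stop and another says give. Recording a reason documents the choice but does not guide it.

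A second reply is that the clause does useful work. Some subjects are extended for other clinical signs. If those signs resolve while ADAMTS13 is stable at or above 10%, the synopsis offers no stop before Day 28 unless there is an upward trend. Section 3.3 supplies one. This stands in full and rules out deleting the clause.

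A third reply is that the 7, 14 and 21 days are calendar subtraction for a hypothetical subject and say nothing about frequency. That is correct.

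A reader might also infer more than the texts support:

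- **That the arms are biased.** The same wording applies to both blinded arms, and nothing in the documents shows that it would act differently in one of them.
- **That the primary result is at risk.** SAP Section 6.1.1 restricts that endpoint to the double-blind daily plasma exchange period, which precedes any extension.
- **That subjects below 10% would be denied an extension at Week 5.** The clause concerns stopping an extension in progress, not starting one.

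**Conclusion.** The point holds, at minor severity. The Section 3.3 stop rule is wrong as written, because it contradicts the synopsis and Table 4 footnote c for one group: subjects on extension, stable below 10%, with no other signs. That group is part of the at-risk population for whom the extension was designed.

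For each such subject, the possible loss is up to 21 days of drug and of open-label eligibility, with the first key secondary window closing earlier by the same amount. The 21 days assume that a site applies the literal reading at Week 6 and that the subject would have stayed below 10% to Week 9. How many subjects would meet these conditions cannot be derived from the documents; it could be none.

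**What to change.** In Protocol Section 3.3 (Decision on treatment extension), insert the words *at or above 10%* directly after *stable*. Leave the upward-trend limb, the condition on other signs and the Day 28 limit as they are.

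Do not delete the clause to match the synopsis. It is Section 3.3's only explicit early stop for subjects extended for other signs whose ADAMTS13 is stable at or above 10%. Without it, some could stay until Day 28, without need, on a drug whose main safety finding is increased bleeding (Section 1.2.5).

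Write to sites to confirm that subjects remaining below 10% should continue, in weekly periods, to at most Day 28 of the extension.

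The cost is one phrase and a site letter, with the notification or approval that Section 4.1 requires for a protocol change. The German-specific protocol version mentioned in the footnote to Section 3.2.2 should be checked for the same sentence. The synopsis, Table 4, SAP, data collection, analysis and sample size need no change.

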3.3.1. RANDOMIZATION

After obtaining oral and written informed consent, subjects will be screened according to the inclusion and exclusion criteria and will receive a unique subject identification (ID) number, assigned by IWRS/IVRS.

At randomization, subjects will be randomized to a caplacizumab or placebo arm in a 1:1 ratio, and will receive a randomization number just prior to study drug administration according to the randomization scheme.

Randomization will be stratified by severity of neurological involvement ($GSC \leq 12$ vs. $GCS=13-15$). Stratification is foreseen to ensure balanced treatment arms for the key secondary endpoints related to neurological involvement and not for the primary endpoint for which the stratification parameter is not known to be relevant.

